4.4.1. Locking the Database

Preparation for locking the ATI001-204 clinical database will occur when all subjects (n=40) have been reviewed and it has been established that there are no outstanding queries to be resolved.

4.5. Populations for Analysis

4.5.1. Screened for eligibility and not treated: (Screen Failures)

Screen Failures are subjects who signed an informed consent and subsequently:

- Did not meet the eligibility criteria of the protocol, or,

- Withdrew consent to be treated before receiving any experimental treatment.

The number of subjects who were screened and not treated will be described in the subject disposition where applicable.

4.5.2. Full Analysis Set (FAS)

The Full Analysis Set (FAS) includes every subject who received at least one dose of any study drug recorded in the Data Management (DM) database excluding screen failures.

4.5.3. Per Protocol (PP)

The per protocol population will comprise subjects who have received Day -7 of cemiplimab, the injection of Ad-RTS-hIL-12 with at least one post IL-12 dose of veledimex, at least one post IL-12 dose of cemiplimab (e.g., Day 15), and who have not had a major protocol deviation for which the key efficacy endpoints could be regarded as confounded or uninterpretable. Subjects who have had minor protocol deviation(s) that are thought not to impact efficacy will be included in this analysis population. Estimates of the overall OS hazard rate, the OS at prespecified timepoints, PFS and the ORR will be based on the PP population.

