16.1. Populations for Analysis

- The safety population will comprise all subjects who have received at least one dose of any of the investigational agents: cemiplimab-rwlc, the injection of Ad-RTS-hIL-12 or any doses of veledimex
- The per protocol population will comprise subjects who have received Day -7 of cemiplimab-rwlc, the injection of Ad-RTS-hIL-12 with at least one post Ad-RTS-hIL-12 dose of veledimex, at least one post Ad-RTS-hIL-12 dose of cemiplimab-rwlc (e.g., Day 15), and who have not had a major protocol violation (i.e., subjects who have had minor protocol violation(s) that are deemed not to impact efficacy will be included in this analysis population.)
- [REDACTED]

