16.5. Efficacy Evaluation

- The primary analysis for efficacy is based on the per protocol population.
- Secondary analyses for all efficacy endpoints will be based on the Safety population.

The primary endpoint for evaluation of efficacy is:

- the estimate of the OS which is performed by estimating the hazard rate based on the accrual and follow-up of all treated subjects.
- The per protocol population will be followed from the first date of treatment up to 24 months for overall survival. Estimates of the single arm hazard rate will be determined and compared with historical control estimates

All populations for analyses and the types of analyses to be performed will be defined in more detail in the statistical analysis plan (SAP).

Secondary endpoints include:

- The OS rate will be determined for 6, 12, 18 and 24 months using a binomial estimate of subjects surviving for at least the amount of time established by the cutpoint.
- PFS, and rate of pseudo-progression (PSP) of Ad-RTS-hIL-12 + veledimex when administered in combination with cemiplimab-rwlc will be determined based on the investigator assessment
- ORR of Ad-RTS-hIL-12 + veledimex when administered in combination with cemiplimab-rwlc at 6, 12, 18 and 24 months will be determined based on an investigator assessment.
- Tumor response rate of Ad-RTS-hIL-12 + veledimex when administered in combination with cemiplimab-rwlc at 6, 12, 18 and 24 months

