16.6.3. Overall Survival

OS is defined as the duration of time from the first dose of study drug (Day -7) to the date of death or to the last follow-up contact date if the subject has not died, in which case the subject is censored if still alive up to 2 years from the first dose of study drug received.

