4.7.1. Overview of Statistical Summaries by Defined Populations

Subject populations will be evaluated and used for presentation and analysis of the following:

- The FAS will be used for summaries of subject disposition, baseline characteristics and for safety. In addition, the FAS will be used in secondary analyses of OS, ORR, and PFS.
- The PP population is to be used for the primary analysis of OS, ORR, PFS and OS.
- When applicable the ESP will be used for analysis of dose limiting toxicities.
- [REDACTED]

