8.1. Primary Efficacy Endpoint

The primary endpoint for evaluation of efficacy is the OS hazard rate which is performed by estimating the hazard rate based on the accrual and follow-up of all treated subjects. Subjects will be followed from the first date of treatment up to 2 years for overall survival.

OS is defined as the duration of time from the first dose of study drug (i.e., cemiplimab at Day - 7) to the date of death from any cause. Censoring will be considered as below:

- Subjects who discontinue study will be censored at date of discontinuation.
- Subjects who are lost to follow-up will be censored at last follow-up contact date.
- If the subject has not died, the subject is censored if still alive up to 2 years from the first dose of study drug received.

All summaries and analyses for the primary efficacy endpoint will be based on per-protocol population.

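### Primary OS is counted from Day -7 but estimated only in subjects who lived to receive a later cemiplimab dose, and the planned all-treated OS analysis has no table in the listed outputs

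*SAP*

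**What the plan says.** **Time origin.** Protocol 16.6.3: "OS is defined as the duration of time from the first dose of study drug (Day -7) to the date of death". SAP 8.1 uses the same origin.

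**Analysis set.** Protocol 16.5: "The primary analysis for efficacy is based on the per protocol population". SAP 8.1: "All summaries and analyses for the primary efficacy endpoint will be based on per-protocol population". SAP 4.5.3 assigns the other main efficacy estimates to PP as well: "Estimates of the overall OS hazard rate, the OS at prespecified timepoints, PFS and the ORR will be based on the PP population".

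**Entry to PP.** Besides the Day -7 dose, the injection and a later veledimex dose, protocol 16.1 requires "at least one post Ad-RTS-hIL-12 dose of cemiplimab-rwlc (e.g., Day 15), and who have not had a major protocol violation". SAP 4.5.3 carries the condition over: "at least one post IL-12 dose of cemiplimab (e.g., Day 15), and who have not had a major protocol deviation".

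**Who the estimate is said to describe.** SAP 8.1 introduces the primary endpoint as "estimating the hazard rate based on the accrual and follow-up of all treated subjects". Protocol 16.3.1 and 16.5 say the same.

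**The all-treated analysis.** SAP 4.7.1: "In addition, the FAS will be used in secondary analyses of OS, ORR, and PFS". SAP 8.2 repeats this for OS, and protocol 16.5 plans secondary efficacy analyses in the Safety population. The visible text of SAP section 10 does not withdraw it. In both visible output lists in the SAP appendices, however, OS Table 14.2.3 is for PP only. The OS Kaplan-Meier figures (14.2.4, 14.2.6) name no population, and FAS survival appears only in by-subject Listings 16.2.6.6 and 16.2.6.8.

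**The concern.** Membership of PP is decided by something that happens about three weeks after the OS clock starts. Until then a future PP member cannot die, so those weeks add person-time and no deaths. A treated subject who dies in that interval is missing from the primary estimate altogether. This is guaranteed (immortal) time, and nothing in either document handles it.

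It also leaves SAP 8.1 saying two things at once. The FAS is the set of subjects who received any study drug (SAP 4.5.2). PP is a selected part of it and cannot be the basis of an all-treated hazard.

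The use made of the estimate is what is at stake. SAP section 8 plans a numerical comparison with historical estimates, and protocol section 16 wants the historical data to be closely matched so that the result can inform further development. No historical series is named, so nobody can check whether it carries a similar survive-to-second-dose condition.

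**Working it through.** **1. Day scale.** SAP 11.5 counts days from Day 0. Protocol 17.4 calls Days -7 through 14 a three-week period: 14 - (-7) = 21 days = 3.0 weeks, which reproduces.

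**2. Guaranteed survival.** Nominal: 15 - (-7) = 22 days, and 22 / 30.4375 = 0.72 month. The ±3-day window on the Day -7 dose gives 19 to 25 days, but not below 21 if the minimum spacing in the protocol Table 1 footnotes is kept. A 14-day toxicity delay takes the nominal 22 days to 36.

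**3. Early-death component.** The inputs from the documents are a median OS of 6 to 7 months in recurrent disease (protocol 6.1) and 40 FAS subjects (SAP 4.4). The early hazard is not given, so it is an assumption: r × L before g = 0.72 month and L afterwards, with the FAS median m held fixed. Then

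- L = ln 2 / (m - g + r·g)
- share dying before g = 1 - exp(-r·L·g)
- PP median = g + ln 2 / L = m + r·g

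| r | Die before g (m = 6 / 7) | Of 40 | Shift in PP median | Relative (m = 6 / 7) |
|---|---|---|---|---|
| 1 | 8.0 / 6.9% | 3.2 / 2.8 | +0.72 month | +12.0 / +10.3% |
| 0.5 | 4.3 / 3.7% | 1.7 / 1.5 | +0.36 month | +6.0 / +5.2% |
| 0.25 | 2.3 / 1.9% | 0.9 / 0.8 | +0.18 month | +3.0 / +2.6% |
| 0 | 0 | 0 | 0 | 0 |

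A 21-day gap gives +0.69, +0.34 and +0.17 month for r = 1, 0.5 and 0.25. If the median were 12.7 months (the sponsor's Phase I 20 mg figure, protocol 6.1), the 22-day shifts would be +5.7%, +2.8% and +1.4%. Measured as deaths over person-time to 24 months, the PP hazard at r = 1 is 8.2 / 7.4% below the FAS hazard.

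**4. Against sampling error.** The approximate 95% interval is median × exp(±1.96 / √events). At a 7-month median with 24 months of follow-up, the death fraction is 1 - exp(-24·ln 2 / 7) = 0.907. That is 36.3 events in 40 subjects, giving 5.1 to 9.7 months, or 22.7 events in 25 subjects, giving 4.6 to 10.6 months. Every shift in the table is smaller than these half-widths.

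**5. Living subjects who are also excluded.** PP drops people who stopped early, missed the injection or had a major deviation. The documents do not size this. As an illustration only, take the planning ratio of 25 evaluable from 36 accrued (protocol 16.2), and let excluded living subjects have later hazard k·L. The PP and FAS medians coincide when L = ln 2 / (m - g) and 2^(-k) = (0.5 - 25/72) / (exp(-r·L·g) - 25/36). For m = 6 / 7 this gives k = 0.49 / 0.58 at r = 1, 0.76 / 0.80 at r = 0.5 and 0.88 / 0.90 at r = 0.25. If the excluded living subjects do better than that, PP falls below FAS.

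**The case against.** PP as the primary set was prespecified in the protocol, and the objective concerns the combination, so describing those who received it is a legitimate question. The SAP text does plan OS in the FAS. No test or threshold depends on the choice. The documents give neither an early-death count nor a PP count, and in subjects with KPS of at least 70 who are fit for resection, r may be well below 1. All of this stands. It limits the weight of the point and supports keeping the PP estimate. It does not remove the guaranteed interval or reconcile PP with an all-treated description. A confidence interval displays sampling error but not a structural offset.

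Three stronger readings are tempting and not supported:

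- **That the FAS analysis was dropped.** The lists still carry response and PFS tables that section 10 withdraws, figures by veledimex dose, and a table for a 20 mg expansion group, although this trial plans a single veledimex dose. They look partly carried over from another study, so a missing table is weak evidence of intent.
- **That PP survival must exceed FAS survival.** Only the early-death component has a fixed direction; step 5 shows that the net can go either way.
- **That the median and quartiles are all that remains of OS** once the fixed-time rates and the parametric estimate are withdrawn. SAP 8.2 keeps a Kaplan-Meier plot, and the lists keep an OS subgroup table and a forest plot.

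**Conclusion.** The point holds as a matter of construction. The primary OS estimate starts at Day -7 in subjects selected for being alive and dosed about 22 days later, has no landmark or delayed-entry rule, and is described as covering all treated subjects when it does not. The absent FAS table is a gap between the SAP text and its output lists.

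The size is conditional. The early-death component lies between 0 and 0.72 month for r between 0 and 1, assuming a piecewise-constant hazard and an FAS median of 6 to 7 months. It is smaller than sampling error, and the net PP-versus-FAS difference is undetermined. Confidence is high about the structure and low about the magnitude. The point should be fixed, but nothing here shows that a conclusion of the trial would change. Nor do the documents show that FAS is the better match to history, since no historical series is named. They support showing both estimates.

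**What to change.** 1. In SAP 4.7.1, 8.1 and 8.2, state that OS in the FAS, from the first dose of any study drug to death from any cause, is the estimate for all treated subjects. Show it beside the PP estimate wherever OS is set against historical figures. Record and date the change in SAP section 10.
2. Add an FAS OS table and an FAS Kaplan-Meier figure next to Table 14.2.3, and name the population on every OS figure.
3. Keep the prespecified PP OS from Day -7, labelled as conditional on receiving a post-injection cemiplimab dose. Add a PP sensitivity analysis in which time at risk starts at that dose (landmark or delayed entry), recorded as an addition to protocol 16.5 and 16.6.3.

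The cost is one table, one figure and one sensitivity run on populations already defined. The change comes late, in an open-label trial whose 40 FAS subjects are already in the database, which is why both estimates should be shown and neither replaced. The all-treated median may come out slightly lower than the PP median.

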4.5.4. Evaluable Safety Population (ESP)

The ESP is a subset of the FAS. Regardless of major protocol deviations, these subjects have received at least one of the following:

- Day -7 of cemiplimab,
- the injection of Ad-RTS-hIL-12 with at least one post IL-12 dose of veledimex,
- and at least one post IL-12 dose of cemiplimab (e.g., Day 15).

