4.4. Data Management

Ziopharm Data Management directs and oversees the administration of the ATI001-204 eCRF database. The clinical trial data from all screened and enrolled subjects populate the ATI001-204 database which is also managed by a third-party contract research organization (CRO). In addition, the ATI001-204 protocol provided for study objectives for which the data obtained are not part of the eCRF. Instead, the data are acquired based on the data transfer agreements (DTA) from 7 external data sources denoted as “vendors” summarized in [Table 1](#) below. Specifically:

- The ATI001-204 clinical database consists of N=40 FAS subjects for whom at least one of the following study treatments were received: Ad-RTS-hIL-12, veledimex, cemiplimab.
- The imaging data objective originally to be undertaken with Bioclinica was put on hold and not performed.

- For completeness it is noted that there are subjects who also have data in the database who are classified as screen failures for whom we are not counting for the purpose of this description. Subjects that were enrolled but did not receive treatment were withdrawn and will not be included in any analysis population.
- A summary of the number of screen failures signing an informed consent is provided in the subject disposition.
- Extraction of Raw SAS datasets from the EDC database will be converted into Study Data Tabulation Model (SDTM) SAS datasets based on CDISC.

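### As written, SAP 4.5.4 admits every subject given Day -7 cemiplimab to the Evaluable Safety Population, so the set is practically the FAS instead of the combination-exposed subset

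*SAP*

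**What the plan says.** SAP 4.5.2 defines the FAS as the set that "includes every subject who received at least one dose of any study drug recorded in the Data Management (DM) database excluding screen failures". SAP 4.4 gives its size: "The ATI001-204 clinical database consists of N=40 FAS subjects".

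SAP 4.5.4 then states "The ESP is a subset of the FAS" and continues "Regardless of major protocol deviations, these subjects have received at least one of the following". Three items follow:

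- "Day -7 of cemiplimab";
- the vector injection with at least one later veledimex dose;
- "and at least one post IL-12 dose of cemiplimab (e.g., Day 15").

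SAP 4.5.3 builds the per-protocol (PP) population from the same three components. There all of them are required, and subjects with a major deviation that confounds efficacy are removed.

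The ESP has two stated uses. SAP 4.7.1 says "When applicable the ESP will be used for analysis of dose limiting toxicities". SAP section 9 puts the main safety analyses on the FAS and adds ESP summaries where applicable. The table lists in the SAP appendices differ from 4.7.1: Table 14.3.13 (Dose Limiting Toxicities) is on the PP population, and Listing 16.2.7.7 (same title) is on the FAS. The readable protocol text (16.1) has a safety population based on any dose of any agent, and no ESP.

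**The concern.** A second safety population is useful only if it isolates the subjects who can inform about the combination. The lead-in asks for any one of the components, and the first of them is the first study drug given. A subject who follows the schedule therefore enters the FAS and the ESP with the same infusion.

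Partial exposure was foreseen. Protocol 9.5 allows replacement of subjects who do not get every study drug, and Protocol 10.8.2 covers the case where the injection is not performed. SAP 4.1 records that nobody was replaced. A subject who received cemiplimab on Day -7 and was never injected would count in the denominator of any ESP toxicity rate while contributing no information on the vector or the combination.

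The wording also contradicts itself, so two programmers could build two different flags: one from the lead-in, the other from the joined list.

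**Working it through.** **1. Figure to reproduce.** The readable SAP gives no ESP count, so there is nothing to reproduce. The sizes available are the FAS of 40 (SAP 4.4), planned accrual of up to 36, and a target of about 25 evaluable for efficacy (both SAP 4.1).

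**2. Membership by exposure pattern.** Describe each subject by five yes/no items: C = Day -7 cemiplimab, V0 = pre-operative veledimex, A = injection, V1 = post-injection veledimex, C2 = post-injection cemiplimab. V1 and C2 require A.

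- Without injection: C and V0 are free, 2 × 2 = 4 patterns.
- With injection: C, V0, V1 and C2 are free, 2 × 2 × 2 × 2 = 16 patterns.
- Total 20. Removing the no-drug pattern leaves **19 FAS patterns**.

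ESP as written is C, or (A and V1), or C2:

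- C = yes: 2 (V0) × (1 without injection + 4 with injection) = 10.
- C = no: injection plus at least one of V1 and C2, 3 × 2 (V0) = 6.
- Total **16**, leaving 19 − 16 = **3** outside.

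ESP read as all components is C and A and V1 and C2, with V0 free: **2** patterns.

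| Rule | FAS patterns admitted (of 19) |
|---|---|
| SAP 4.5.4 as written | 16 |
| All components required | 2 |

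These are counts of possible patterns, not of subjects. The three patterns in the FAS but outside the ESP are pre-operative veledimex only; injection only; and both of these with no later dose. All three lack Day -7 cemiplimab.

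**3. Effect on schedule.** SAP 8.1 and 8.3.2 both identify the first dose with cemiplimab at Day -7. All 10 patterns with that dose are in the ESP. Only 2 of the 10 have the full combination. Another 2 never reached the vector (cemiplimab alone, or with pre-operative veledimex).

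**4. Which reading was meant.** Three features point to all components:

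- The last item opens with a joining word that does not fit an any-one-of lead-in.
- The items repeat the PP exposure criteria, which are joint.
- Setting deviations aside makes sense as PP without its deviation rule. It adds nothing to an any-dose set, because the FAS already ignores deviations.

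**5. Size.** Let *n* of 40 be fully treated with DLT rate *q*, and let the others have rate *r*. Assume all 40 are in the ESP as written. The ESP rate relative to the fully treated rate is

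[*nq* + (40 − *n*)*r*] / (40*q*).

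With *r* = 0 this is *n*/40:

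| Fully treated (assumed) | Factor |
|---|---|
| 25 | 25/40 = 0.625 |
| 35 | 35/40 = 0.875 |
| 40 | 40/40 = 1 |

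With *r* = *q* the factor is 1, and with *r* above *q* it exceeds 1. The documents give neither *n* nor *r*.

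**6. What does not depend on the ESP.** The toxicity boundary (Protocol 16.2, SAP 4.1) counts subjects who reach Day 30 and meet the Stopping Rules. The efficacy estimates use PP and FAS (SAP 4.7.1).

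**The case against.** The case for treating this as minor is fair. Both uses of the ESP are conditional, the FAS is the main safety set, and no table or listing in the readable appendices is assigned to the ESP. The DLT table is on the PP population, which already requires all components, so as specified it contains no under-exposed subject. A careful programmer might also read the list as joint.

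Most of that stands, and it limits the consequence. It does not rescue the definition: the SAP text still names the ESP as the DLT population, and the rule as worded builds the wrong set. The appendices also expose a second problem, because DLTs are assigned to three populations: ESP in 4.7.1, PP in the table, FAS in the listing.

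Two stronger readings are tempting, and the documents do not support them.

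- A reader might infer that the ESP and FAS are identical. They are not strictly so, because the three off-schedule patterns above are in the FAS only.
- A reader might take 25 evaluable out of 36 accrued and conclude that the DLT rate is cut to 25/36 = 0.69 of its true value. But 36 is planned accrual where the SAP reports 40 treated, 25 is a target for efficacy evaluability and not a count of fully treated subjects, and the factor would apply to no DLT table that the SAP specifies.

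**Conclusion.** The definition in SAP 4.5.4 is wrong as written. Every FAS subject with Day -7 cemiplimab qualifies, so the ESP is practically the FAS of 40. Any summary run on it would mix fully exposed subjects with subjects who never received the vector or the combination.

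How far that would move a DLT rate cannot be determined. The factors 0.625, 0.875 and 1 are illustrations that rest on assumed numbers fully treated, on no DLT among the rest, and on all 40 being in the ESP. If incomplete treatment was itself caused by toxicity, the shift could be smaller or could reverse.

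It would be wrong to infer that the stopping boundary, a stopping decision or the survival estimate is compromised, since none of them uses this population. This is a contradiction in a supplementary safety set that should be corrected, together with the unreconciled DLT population.

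**What to change.** 1. In SAP 4.5.4, change the lead-in so that a subject must have received *all* of the listed components, still regardless of major deviations.
2. Report the ESP count in the disposition table. SAP 5.2 visibly names the PP population there and the next item is blacked out, so confirm that the ESP is included.
3. Choose one DLT population and use it in SAP 4.7.1, Table 14.3.13 and Listing 16.2.7.7.
4. Show the DLT rate beside the rate on the FAS. An all-components rule drops subjects whom toxicity stopped before the post-injection cemiplimab dose, and the FAS column keeps them in view.
5. Add a clause retaining subjects who had a DLT before completing the components only if the SAP also defines DLT. The readable text does not define it for this trial, so the clause could not be programmed as things stand.

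The cost is a few words of SAP text, one re-derived population flag, aligned headers on one table and one listing, and an extra column. No new data are needed.
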